12. STATISTICAL METHODS AND SAMPLE SIZE DETERMINATION BY ASTRAZENECA

12.1 Description of analysis sets

12.1.1 Full analysis set

All patients who have been randomised to study treatment will be included in the full analysis set (FAS) irrespective of their protocol adherence and continued participation in the study. Patients will be analysed according to their randomised study medication irrespective of whether the event occurred before or following discontinuation of study medication. Patients who withdraw consent to participate in the study will be included up to the date of their study termination except for vital status known through public records (for use in the analysis of all cause death). All efficacy variables will be analysed using the FAS.

12.1.2 Safety analysis set

All patients who received at least 1 dose of randomised ticagrelor or placebo, will be included in the safety analysis set. Throughout the safety results sections, erroneously treated patients (e.g., those randomised to ticagrelor but actually given placebo) will be accounted for in the actual treatment group. A patient who in error has received both ticagrelor and placebo will be accounted for in the randomised treatment group.

12.2 Methods of statistical analyses

This section provides a summary of the planned statistical analyses. Further details will be provided in a Statistical Analysis Plan.

12.2.1 Efficacy analysis

All efficacy analyses will be based on the ITT principle using the FAS, including only adjudicated endpoint events. Investigators are instructed to report all potential endpoint events in the eCRF, even those that may not meet strict endpoint definitions, to ensure all potential events are reviewed and adjudicated by the CEC.

For time to event variables, treatments will be compared using a Cox proportional hazards model with a factor for treatment group, using the Efron method for ties. Censoring principles are described in Section 12.2.4. The p-value (calculated using the Wald test), hazard ratio (HR) and 95% confidence interval will be reported. Kaplan-Meier estimates of the cumulative risk will also be presented.

The family wise error rate will be controlled for the primary and secondary efficacy analyses by applying a hierarchical test sequence as described in Section 12.2.1.2. No other adjustments for multiple comparisons will be made.

As supportive analyses, data from patients with diabetes in PEGASUS (patients with MI within 1-3 years) and EUCLID (PAD patients) will be pooled and analyzed with and without

data from this study. These analyses will be described in a separate SAP and reported separately.

12.2.1.1 Primary efficacy variable

The primary efficacy variable, time from randomisation to the first occurrence of any event from the composite of CV death, MI or stroke, will be analysed using the methodology described in Section 12.2.1. The null hypothesis of no treatment effect,

H_0 : HR (ticagrelor divided by placebo) = 1,

vs. the alternative hypothesis,

H_1 : HR \neq 1,

will be tested at 4.96% two-sided significance level.

The assumption of proportional hazards will be assessed visually using log-cumulative hazard plots. The effect of any departures from proportional hazards will be discussed as part of the presentation of results.

To assess possible effects of missing data, sensitivity analyses will be done as follows. The event rate in the placebo arm will be used to estimate the intensity of a Poisson process. Based on the missing follow-up time, i.e. the time from censoring to PACD, the expected number of events in the ticagrelor group that could have been observed if the patients had completed the study will be estimated from the Poisson process. The comparison of ticagrelor and placebo will be recalculated with these additional events. If the result is still significant with these additional events, the intensity of the Poisson process will be increased and events will be added to the ticagrelor group until the primary analysis is non-significant.

Subgroup analyses on the primary efficacy variable will be performed to evaluate variation of treatment effect. Relevant subgroups, eg age, sex, race, ASA use and medical history, will be examined. Hazard ratios and 95% confidence intervals will be reported for each subgroup as well as p-values for the tests of interaction between treatment and each subgroup.

12.2.1.2 Secondary efficacy variables

The secondary efficacy variables will be analysed using the methodology described in Section 12.2.1.

- 1. Time from randomisation to death of CV cause
- 2. Time from randomisation to first occurrence of MI
- 3. Time from randomisation to first occurrence of ischaemic stroke
- 4. Time from randomisation to death of any cause.

Endpoints 1-4 will be included in the confirmatory testing procedure. Only if the treatment effect on the primary efficacy variable is significant at the 4.98% level, will the secondary efficacy variables be tested in a confirmatory sense in the order given above. The hypothesis testing will continue at the 4.98% significance level until the first statistically non-significant treatment difference ($p \geq 0.0498$) is observed.

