All efficacy analyses will be based on the intention to treat (ITT) principle using the full analysis set (FAS) including only adjudicated endpoint events. For time to event variables, treatments will be compared using a Cox proportional hazards model with a factor for treatment group. The p-value, hazard ratio (HR) and 95% confidence interval will be reported. Kaplan-Meier estimates of the cumulative risk will also be presented. The family wise error rate will be controlled for the primary and secondary efficacy analyses by applying a hierarchical test sequence.

The final primary treatment comparison will be made at a significance level of 4.96%, adjusted for the planned efficacy interim analysis. Assuming a true hazard ratio of 0.84 between ticagrelor and placebo, 1385 primary endpoint events will provide a power of 90%. With an annual event rate of 2.5% in the placebo treatment group, 19000 patients, randomised in a 1:1 ratio, are estimated to provide the required number of primary events after receiving study medication for an anticipated average of 40 months.

TABLE OF CONTENTS	PAGE
TITLE PAGE	1
PROTOCOL SYNOPSIS.....	2
TABLE OF CONTENTS.....	6
LIST OF ABBREVIATIONS AND DEFINITION OF TERMS	11
1. INTRODUCTION	15
1.1 Background	15
1.1.1 Medical need.....	15
1.1.2 Role of antiplatelet therapy in patients with DM.....	15
1.1.3 Product background	16
1.1.4 Ticagrelor in patients with DM.....	17
1.2 Research hypothesis.....	17
1.3 Rationale for conducting this study	17
1.4 Benefit/risk and ethical assessment.....	18
2. STUDY OBJECTIVES.....	19
2.1 Primary objective	19
2.2 Secondary objectives	20
2.3 Exploratory objectives	20
2.4 Safety objective.....	20
3. STUDY PLAN AND PROCEDURES	21
3.1 Overall study design and flow chart	21
3.2 Rationale for study design, doses and control groups.....	28
4. PATIENT SELECTION CRITERIA.....	29
4.1 Inclusion criteria	29
4.2 Exclusion criteria	30
5. STUDY CONDUCT	31
5.1 Restrictions during the study	31
5.2 Patient enrolment and randomisation.....	31
5.2.1 Procedures for randomisation	32
5.3 Procedures for handling patients incorrectly enrolled or randomised	32
5.4 Blinding and procedures for unblinding the study.....	33

5.4.1	Methods for ensuring blinding.....	33
5.4.2	Methods for unblinding the study.....	33
5.5	Treatments.....	34
5.5.1	Identity of study medication(s).....	34
5.5.2	Doses and treatment regimens.....	34
5.5.3	Development of indication for ADP receptor antagonist during study.....	35

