12.2.3 Interim analysis for efficacy

An interim analysis will be performed by the DMC. The interim analysis will be performed following the accrual and confirmation by adjudication of 517 primary events. The stopping boundary at the interim analysis is a 2-sided p-value <0.001 for both the primary endpoint (CV death, MI, or stroke) and for the CV death endpoint (the 1st secondary efficacy endpoint). The interim p-value is small enough for the final analysis to be conducted at a significance level of 4.96%, with the family wise error rate controlled at 5.00%. These boundaries were determined using a Haybittle-Peto procedure (Haybittle 1971, Peto et al 1976).

If a recommendation to stop the study is made at the interim, all subsequent testing will be done at the same significance level as for the interim.

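### Protocol 12.2.1.2 gates and tests the secondary endpoints at 4.98%; every other statement of the final level, in protocol and SAP, is 4.96%, and SAP section 6 does not record the difference

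*Protocol*

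**What the plan says.** Protocol 12.2.1 states that family-wise error for the primary and secondary efficacy analyses is controlled "by applying a hierarchical test sequence as described in Section 12.2.1.2". Section 12.2.1.2 is therefore where the protocol defines the confirmatory sequence, and it gives the level three times:

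- the gate: "Only if the treatment effect on the primary efficacy variable is significant at the 4.98% level, will the secondary efficacy variables be tested";
- the tests themselves: "The hypothesis testing will continue at the 4.98% significance level until the first statistically non-significant treatment difference";
- the stopping condition in decimal form, p ≥ 0.0498.

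The other protocol statements of the final level are all 4.96%. The synopsis says: "The final primary treatment comparison will be made at a significance level of 4.96%, adjusted for the planned efficacy interim analysis". Section 12.2.1.1 says of the primary null hypothesis that it "will be tested at 4.96% two-sided significance level". Sections 12.2.3 (interim analysis) and 12.3 (sample size) give the same value, and 12.2.3 ties it to a family-wise error of 5.00%.

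The SAP uses 4.96% for the final analysis in sections 1.3, 4.2.1, 4.2.3 and 5. Section 4.2.3 is the counterpart of protocol 12.2.1.2; it applies 4.96% to both the gate and the secondary tests and stops at p ≥ 0.0496. SAP section 6 mentions only added exploratory objectives.

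**The concern.** The discrepant value sits in the rule that decides which claims are confirmatory. It appears in both percent and decimal form, so it is not a single slipped digit. Two results would be read differently depending on the section or document followed:

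- **Primary p from 0.0496 to below 0.0498.** Not significant under protocol 12.2.1.1, but counted as significant in 12.2.1.2 for opening the secondary sequence.
- **Secondary p in the same band.** A confirmatory claim under the protocol, not under the SAP.

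A pre-specified threshold should have one value before the data are unblinded. Where the SAP departs from the protocol's written threshold, its section on changes is the place to say so.

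**Working it through.** **Inputs.** Protocol 12.2.3: interim look at 517 primary events, stopping at a "2-sided p-value <0.001 for both the primary endpoint (CV death, MI, or stroke) and for the CV death endpoint"; intended family-wise error 5.00%. Protocol 12.3: 1385 final events, hazard ratio 0.84, power 90%, 1:1 allocation. Final level: 4.96% or 4.98%.

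**1. Reproduce the plan's 4.96%.** Treat the primary as tested at both looks. The information fraction is t = 517/1385 = 0.373, so the correlation between the interim and final statistics is √t = 0.611. With c₁ = 3.2905 (two-sided 0.001) and c₂ the final critical value, the overall error is

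1 − ∫ from −c₁ to c₁ of φ(x)·[Φ((c₂ − √t·x)/√(1−t)) − Φ((−c₂ − √t·x)/√(1−t))] dx.

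| Final level | c₂ | Overall error |
|---|---|---|
| 4.96% | 1.9634 | 4.9999% |
| 4.98% | 1.9617 | 5.020% |

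Solving for exactly 5.00% gives a final level of 0.04960. The plan's 4.96% reproduces.

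**2. A likely origin of 4.98%.** The SAP amendment history records a superseded design with the interim at 375 of 750 events. At t = 0.5 the same calculation gives 0.04978, or 4.98%. The value may be a leftover from that design. This is an inference from the arithmetic; the documents do not say so, and the point does not depend on it.

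**3. Effect on the primary comparison.** With 1385 events and 1:1 allocation, the critical hazard ratio is exp(−2c₂/√1385):

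- 4.96%: exp(−2 × 1.9634/37.216) = 0.89986
- 4.98%: exp(−2 × 1.9617/37.216) = 0.89994

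Power at hazard ratio 0.84 is Φ(|ln 0.84|·√1385/2 − c₂) = Φ(3.2443 − c₂), which is 89.99% and 90.02%. The difference, about 0.03%, is the probability that the primary falls in the disputed band.

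**4. Error of the rule as written, both nulls true.** The 5.020% in step 1 is not this error. Stopping needs p < 0.001 on the primary and on CV death together, and the primary itself is still declared at 4.96%. Simulation (40 million replicates, Monte Carlo standard error 0.0034 percentage points) assumed the same 37.3% information for CV death and a range of correlations between the endpoints, neither of which the documents give:

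| Assumed correlation | Gate and CV death at 4.98% | At 4.96% |
|---|---|---|
| 0 | 4.959% | 4.958% |
| 0.3 | 4.960% | 4.958% |
| 0.5 | 4.966% | 4.963% |
| 0.7 | 4.976% | 4.972% |
| 0.9 | 4.982% | 4.976% |

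A direct check agrees. The extra error is roughly the band width (0.02 percentage points) times the chance that CV death is significant given a primary result in the band: 0.02 × 0.0498 = 0.001 points at correlation 0, and 0.02 × 0.327 = 0.007 points at 0.9.

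**5. Null CV death, primary effect so large that the gate always opens.** CV death is then effectively tested at 0.001 at the look and at the secondary level at the end. The formula in step 1 applies with t set to the CV death information fraction, which is again an assumption:

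| CV death information at the look | 4.98% | 4.96% |
|---|---|---|
| 30% | 5.031% | 5.011% |
| 37.3% | 5.020% | 5.000% |
| 50% | 5.002% | 4.983% |
| 60% | 4.991% | 4.972% |

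The error exceeds 5.00% when that fraction is below about 52% with 4.98%, and below about 37% with 4.96%.

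**The case against.** The strongest reply is that the matter is already settled in practice. Protocol 12.2 calls itself a summary and adds: "Further details will be provided in a Statistical Analysis Plan". The SAP is later (September 2018, against February 2017), states the gate and the secondary tests at 4.96%, and is the stricter of the two. Any confirmatory claim it allows is also allowed by the protocol, so following the SAP adds no error. A reader of the protocol alone can also see from 12.2.3 that 4.96% is the derived figure. On this view the 4.98% is an editorial remnant.

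Much of that stands: the SAP analysis needs no change, and the numerical consequence is negligible. It is also true that 4.96% does not guarantee 5.00% in every configuration, as step 5 shows; the correction narrows the range of excess without removing it. What does not follow is that nothing needs doing. Supplying further detail is not the same as overriding a stated significance level, and neither document says that the SAP prevails. Protocol 12.2.1 names 12.2.1.2 as the place where error is controlled, and the SAP section meant to record departures omits this one.

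**Conclusion.** The concern holds. Protocol 12.2.1.2 carries a level that conflicts with the rest of the protocol and with the SAP, and the difference is not disclosed. The protocol's own interim design supports 4.96%.

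The consequence is very small. The band is 0.0002 wide. With both nulls true, the 4.98% gate adds 0.001 to 0.007 percentage points to a total that stays below 5.00% over the assumed correlations of 0 to 0.9. The largest figure found is 5.031%, in the always-open-gate case with an assumed 30% CV death information at the look. The contradiction itself rests on the text alone; only the sizes depend on the assumed correlation and information fractions. It should be fixed because it is a pre-specified decision threshold with two values, not because error control is materially at risk.

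**What to change.** In protocol 12.2.1.2, replace 4.98% (twice) and 0.0498 (once) with 4.96% and 0.0496. At minimum, add a sentence to SAP section 6, before unblinding, stating that the 4.96% in SAP 4.2.3 supersedes the 4.98% in protocol 12.2.1.2 for both the gate and the secondary tests.

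The SAP note costs one line and changes no analysis. The protocol edit is equally short, but it goes through protocol 8.5: a substantial change needs an amendment with ethics approval and, where applicable, regulatory approval, and an administrative change may have to be communicated to or approved by ethics committees where local rules require. If no further amendment is planned, the SAP note is the proportionate route.

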12.2.1.3 Exploratory variables

Other objectives are exploratory, with the purpose of comparing other long-term treatment effects of ticagrelor vs. placebo.

Time to event variables will be analysed using the methodology described in Section [12.2.1](#):

- Time from randomisation to first occurrence of any event from the composite of all- cause death, MI or stroke
- Time from randomisation to first occurrence of stroke
- Time from randomisation to first occurrence of any event from the composite of all- cause mortality, MI, stroke, intracranial haemorrhage and fatal bleeding (irreversible harm events).

Descriptive reporting of the resource utilisation data and health related quality of life data based on the EQ-5D are to be documented in the CSR. The data will be combined with economic data and life expectancy data collected independently of the study to construct comparative health economic analyses between treatment groups. The economic analysis and cost-effectiveness analyses that include data external to the study will not be included in the CSR.

12.2.2 Safety variables

All analyses of safety variables will be based on the safety analysis set as described in Section [12.1.2](#).

12.2.2.1 Bleeding events

Analysis of time from randomisation to each of the following endpoints will be performed using the methodology described in Section [12.2.1](#):

- Time to first TIMI Major bleeding event
- Time to first TIMI Major or minor bleeding event
- Time to first PLATO major bleeding event
- Time to permanent discontinuation of study medication due to any bleeding event.

The assessment of time to bleeding events will focus on the items above but will also include analysis of time to first adjudicated event for additional categories of bleeding according to

the TIMI, PLATO and BARC definitions. Exploration of potential risk factors for bleeding events will be performed. All AEs relating to bleeding will be summarised separately and the total number of bleeding events will be assessed. Exploration of potential risk factors for AEs that are increased with ticagrelor dosing may be done.

12.2.2.2 SAEs and AE of interest

AEs of interest, DAEs as well as SAEs will be evaluated. Summaries, by system organ class and preferred term using MedDRA, will be presented by treatment group using descriptive statistics.

12.2.3 Interim analysis for efficacy

An interim analysis will be performed by the DMC. The interim analysis will be performed following the accrual and confirmation by adjudication of 517 primary events. The stopping boundary at the interim analysis is a 2-sided p-value <0.001 for both the primary endpoint (CV death, MI, or stroke) and for the CV death endpoint (the 1st secondary efficacy endpoint). The interim p-value is small enough for the final analysis to be conducted at a significance level of 4.96%, with the family wise error rate controlled at 5.00%. These boundaries were determined using a Haybittle-Peto procedure (Haybittle 1971, Peto et al 1976).

If a recommendation to stop the study is made at the interim, all subsequent testing will be done at the same significance level as for the interim.

12.2.4 Censoring

The EC will monitor the accrual of the number of primary events and when appropriate predict and define a PACD at which time the pre-defined target number of events for the primary composite endpoint are expected to have occurred.

The PACD will be the common date at which all patients who are event free for the given endpoint and have not withdrawn consent for participating in the study will be censored in efficacy time-to-event analyses. Events that occur after the PACD but before the SCV will also be collected and adjudicated. These events will be included in sensitivity analyses but not in the primary analysis.

Patients who have not had the event(s) in question will be censored at the earlier of (1) the PACD and (2) the last study contact when all components of the endpoint in question were assessed. In the analysis of CV death and composites including CV death censoring will occur at the earliest of (1), (2) and (3) the date of death from non-cardiovascular causes. For endpoints not including death, all deaths are censoring events. In safety time-to-event analysis of bleeding, patients not having suffered any bleeding event in the given category will be censored at the earlier of SCV, 7 days after last dose of study drug, death, last contact or withdrawal of consent.

Complete endpoint information will be pursued with every effort for all patients regardless of their study medication status, unless they exercise their right to withdraw consent. Patients

who have a non-fatal event will continue study follow-up. For patients who withdraw consent and for whom only vital status (known to be alive at study closure, or date of death) may be obtained from public records, the occurrence of all components of the primary endpoint cannot be assessed. Thus, in the main analyses patients will be censored at the time of consent withdrawal. However, the determination of all-cause death will utilise all publicly known mortality data, even that extending beyond date of consent withdrawal. The vital status information will be included in the analysis of all cause death as a single endpoint, in sensitivity analysis and tabulations.

Similarly, complete information on the primary endpoint may not be obtained for patients who are lost to follow-up (LTFU). Any such patient will be censored in the analysis of the primary composite endpoint at the last contact where all elements of the endpoint were assessed. A patient will not be recorded as LTFU until the end of the study, after every allowable effort to get in contact has been made. Hence, it is anticipated that the number of patients LTFU will be limited.

12.3 Determination of sample size

Based on clinical studies and epidemiological information, the event rate for the composite of CV death, MI or stroke has been estimated to be 2.5% annually in a population consisting of patients with T2DM at high risk of CV events without medical history of previous MI or stroke.

The final primary treatment comparison will be made at a significance level of 4.96% adjusted for the planned efficacy interim analysis. Assuming a true hazard ratio of 0.84 between ticagrelor and placebo, 1385 primary endpoint events will provide a power of 90%.

With an annual event rate of 2.5% in the placebo treatment group, 19000 patients, randomised in a 1:1 ratio, with an average follow-up period of 40 months, are estimated to provide the required number of primary events. The expected minimum follow-up period is 29 months, based on an enrolment period of 28 months.

The expected number of patients who will be lost-to-follow-up is negligible and hence not considered in the determination of samples size.

12.4 Independent Data monitoring committees

12.4.1 Clinical Endpoint Committee (CEC)

See Section [5.10.3](#).

12.4.2 Data Monitoring Committee (DMC)

See Section [5.10.4](#).

13.2 Overdose

An overdose of study medication is defined as intake of more than 360 mg ticagrelor/ticagrelor placebo per day. In the event of an overdose of study medication ascertain the time and extent of the overdose regardless of severity. Determine the causative circumstance and whether haemorrhagic or toxic complications have occurred or are likely to do so. Depending on these facts it has to be decided if the patient should be hospitalised for observation or not. Bleeding is one of the most likely pharmacological effects of excessive ticagrelor dosing, and appropriate supportive measures such as volume replacement, local haemostatic measures (eg, compression), and decompression or drainage may be required depending on the localisation, extent of bleeding or volume of blood lost. Patients with overdose-related bleeding should be cautioned to avoid unnecessary activity, mechanical tissue stress, and minor trauma for at least 24 hours after the bleeding has stopped. The IB documents other symptoms that can be expected after an overdose of ticagrelor..

- An overdose with associated AEs is recorded as the AE diagnosis/symptoms on the relevant AE modules in the eCRF and on the Overdose eCRF module.
- An overdose without associated symptoms is only reported on the Overdose eCRF module.

If an overdose on an AstraZeneca study drug occurs in the course of the study, then investigators or other site personnel inform appropriate AstraZeneca representatives immediately, or **no later than 24 hours** of when he or she becomes aware of it.

The designated AstraZeneca representative works with the investigator to ensure that all relevant information is provided to the AstraZeneca Patient Safety data entry site.

For overdoses associated with SAE, standard reporting timelines apply, see Section 6.4.4. For other overdoses, reporting should be done within 30 days.

